D.9.6. Future developments in HCV treatment. Study participants will receive state-of-the-art treatment (IFN in combination with telaprevir and ribavirin). As additional regimens become available with either more convenient dosing, fewer side effects, or increased efficacy, participants in all 3 arms will receive treatment according to best available practices. On October 10, 2014, the FDA approved fixed-dose (ledipasvir and sofosbuvir). Because rates of SVR are >95% in patients initiating treatment with fixed-dose (ledipasvir and sofosbuvir), all newly enrolled subjects will initiate treatment with this regimen. It is likely that our intensive models of care will be generalizable to IFN-sparing regimens which include only oral therapies. We recognize that HCV treatment has been greatly simplified, but issues with adherence, resistance, side effects, and cost will remain.

D.10. Data sources and collection.

D.10.1. Overview. Sources of data will include: blood and urine tests, participant interviews, medical charts, staff activity and expense logs, direct observation of staff, and electronic adherence monitors (Table 3).

D.10.2. Research visits. Research visits will occur at baseline, then every 4 weeks during the first 12 weeks of treatment, then at week 24 (if necessary), a “Final Treatment Week visit” will be conducted after the last day of treatment, and then post-treatment visits after 4, 12, and 24 weeks, for a total of up to 9 research visits. Participants will receive \$25 for each visit and an additional \$20 for visits with blood draws.

Baseline visit (Table 3). At baseline we will assess: sociodemographic and HCV clinical factors, potential mediating variables based on the IMB model, potential moderators (including psychiatric status, substance use, and unstable housing), and additional psychosocial factors hypothesized to predict adherence. The baseline visit will take approximately 3 hours. Blood will be collected at the first visit and stored for possible HCV viral load and resistance testing, and for future studies.

Follow-up visits (Table 3). Follow up visits will occur at weeks 4, 8, 12, and 24 (if necessary).

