Adherence to all medications will be evaluated by electronic monitors and self-report. Weeks on treatment will be determined by electronic monitors and chart review. HCV viral load, virological endpoints, and resistance results will be obtained by chart review and blood draw, if unavailable by chart review. IMB model mediators will be assessed at weeks 8 and 12. Potential moderators will be assessed at each monthly visit.

Table 3. Overview of Data Collection by Aims

Aim & Hypothesis	Construct	Measure, source	Research visit (week)	Source
Outcome Measures				
Aim 1, H1	Adherence	Med-ic® and MEMS® Electronic Monitors	4,8,12	Electronic
Aim 1, H2	Completion	Medical record	NA	Chart
Aim 1, H3	Viral load (SVR)	HCV VL by Roche TaqMAN assay	0,4,8,12, 24, FU 4, FU12, FU24	Chart, Blood
Aim 1/2, H4	Resistance	HCV GenoSURE NS3/4A, NS5A, NS5B (Monogram)	4, 8, 12, 24, FU4, FU12, FU24	Chart, Blood
Aim 3	Cost	HCV treatment mDOT and CGT interventions Non-HCV treatment health services	NA NA 12,24, FU4, FU12, FU24	Chart Logs, Direct Observation Q
Other covariate measures*				
All	Demographics	Age, race/ethnicity, education, income, housing	0	Q
All	HCV-related clinical information	HCV VL, HIV, HCV genotype/subtype, IL28B, APRI and FibroSURE (biomarkers of liver fibrosis)	0	Chart
All	Substance use	Addiction severity Index-Lite (ASI-lite) (152,153) Alcohol use (AUDIT) (154) Urine toxicology EMIT assay	0,4,8,12, 24, FU4, FU12, FU24	Q, Urine
All	Methadone dose opiate withdrawal	Methadone dose; Subjective and Objective Opiate Withdrawal Scales (SOWS and OOWS) (155)	0,4,8,12, 24, FU4, FU12, FU24	Q
All	Neuropsychiatric	MINI (138-140)	0	Q
All	Information, motivation, and behavioral Skills	Health Beliefs Model (161) HCV Motivation (161) Adherence Self-Efficacy (161)	0, 12	Q
All	Social support	Medical Outcomes Scale (162)	0,4,8,12,24, FU4, FU12, FU24	Q
All	DAA levels	GC-MS (if additional funding obtained)	4	Blood
All	Depression, anxiety, and hostility	Depressive symptoms (BDI-II) (156-157) Brief Symptom Inventory (BSI) anxiety subscale (158) BSI hostility subscale (158-160)	0,4,8,12,24, FU4, FU12, FU24	Q
All	Psychosocial factors	Stages of readiness for HCV treatment (183) Trust in physician (184)	0 0,4,8,12,24, FU4, FU12, FU24	Q
All	Quality of life	HCV QOL and EQ-5D (163-166)	0,4,12, 24, FU4, FU12, FU24	Q
All	Med side-effects	Adult ACTG adherence instrument – revised (167)	0,4,8,12, 24, FU4, FU12, FU24	Q

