using prevailing national wage rates to determine the cost of the time, and applying this cost to each DOT interaction. Patient time costs will be valued based on the minimum wage, because most patients are likely to be unemployed. The cost of the CGT intervention will be similarly determined through observational studies, as well as staff member time and activity logs, and expense logs will be maintained for transportation and other incidental costs. Provider time spent on research activities, such as conducting research visit assessments, will be excluded. We will also examine the cost of health care services received outside of the study (emergency department visits, hospitalizations, substance abuse treatment) based on quarterly patient self-reports.

D.10.4. Data Sources. There will be 6 data sources. Results will not be provided to participants' medical providers unless participants specifically request (in writing) that study staff release this information.

Medical record. HCV viral load and resistance assays (if no SVR) will be obtained when possible by chart review. HCV viral load is measured by the Roche TaqMAN assay and HCV resistance is measured by the Monogram HCV GenoSURE NS3/4A assay, which is automatically run on any HCV viral load which is ≥ 2000 IU/ml. Information on treatment interruptions and discontinuation will be obtained from medical records.

Blood. Three tubes of blood will be drawn at weeks 0, and 4, and stored at Einstein's Clinical Research Center (CRC). HCV viral load and resistance assays will be performed if not available by chart review. For subjects who fail to achieve SVR, resistance testing will be performed on post-treatment specimen. All testing will be performed at Montefiore's laboratories.

Urine toxicology. Participants will provide urine specimens at each research visit, which will be tested for cocaine and opiates (and pH to ensure validity) using enzyme multiplied immunoassay technique.

Adherence by electronic monitors (Med-ic® and MEMS®) and self-report.

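### The general non-release rule in D.10.4 does not exempt study-run HCV viral load or resistance results, so a finding made only by the study could by default be unknown to the on-site HCV clinician (minor fix)

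*Combined protocol and SAP*

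**What the plan says.** D.10.4 (Data Sources) announces six sources and, before describing any of them, states: "Results will not be provided to participants' medical providers unless participants specifically request (in writing) that study staff release this information". The rule speaks of results in general. It does not name viral load or resistance, and it does not exempt them.

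The chart comes first for virology. Under Medical record, D.10.4 says: "HCV viral load and resistance assays (if no SVR) will be obtained when possible by chart review". The study fills gaps. D.10.2 says: "HCV viral load, virological endpoints, and resistance results will be obtained by chart review and blood draw, if unavailable by chart review", and the Blood paragraph of D.10.4 repeats it: "HCV viral load and resistance assays will be performed if not available by chart review". That paragraph adds: "For subjects who fail to achieve SVR, resistance testing will be performed on post-treatment specimen".

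Table 3 gives chart and blood jointly as the source for viral load and resistance, with visits through follow-up week 24. D.8 places HCV care on site in all three arms, so the on-site HCV clinician is one of the medical providers the rule covers. The one disclosure of health information by study staff for safety in the supplied text is the D.5 consent item on psychiatric distress.

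**The concern.** The study runs an assay when its chart review finds no result. A study-run result is thus likely to be one the treating clinician does not have, and the default is not to pass it on. Release depends on the participant asking in writing. The supplied text does not say that participants are told their study results or invited to make that request.

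What is at stake is the care of a few people: someone viraemic after treatment, or carrying a new resistance mutation, whose clinician is not told. The protocol treats resistance as relevant to retreatment, though only as an input that D.12.6 varies in the cost-effectiveness model. It describes no care pathway that turns on a study-run result.

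**Working it through.** This is mainly a reading of the text. The only arithmetic gives the size of the group from which affected participants would come.

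**1. Does the rule reach virology?** It stands at the head of D.10.4, above medical record, blood, urine toxicology, adherence monitoring and surveys. Blood is one of the listed sources and none is carved out. As written, yes.

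**2. Can a study-only virology result arise?** Yes, under the fallback in D.10.2 and D.10.4. It is plausible after treatment as well: Table 3 lists blood through follow-up week 24, D.10.2 pays extra for visits with a blood draw, and D.6 describes active tracking. A participant who has drifted from clinical care may still attend a research visit.

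**3. What narrows it?**
- The chart is used where possible, and chart results are already visible to the clinician.
- The only scheduled stored samples are described by "Three tubes of blood will be drawn at weeks 0, and 4". Those cannot show post-treatment failure.
- The post-treatment specimen used for resistance testing is not said to be a research sample.
- D.10.4 says a resistance assay runs automatically on any viral load of 2000 IU/ml or more. A participant with a clinical viral load at that level needs no study action. D.10.4 names only the NS3/4A assay here, whereas Table 3 also lists NS5A and NS5B, so this route is not shown to cover every planned resistance result. It does not help where no clinical viral load was drawn.
- D.10.4 states: "All testing will be performed at Montefiore's laboratories". Some results might reach the clinical record that way, but the text does not say so.
- The on-site clinician can order a missing viral load.

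**4. Size of the source group (participants without SVR).** D.7 plans 150 participants, 100 of them on ledipasvir/sofosbuvir, leaving 150 − 100 = 50 on earlier regimens.
- Ledipasvir/sofosbuvir, SVR above 95% (D.9.6): 100 × (1 − 0.95) = 5, so fewer than 5 without SVR.
- Earlier regimens at the 75% SVR of the telaprevir trial in B.3: 50 × 0.25 = 12.5.
- Earlier regimens at the D.13 planning rates, assuming equal allocation within these 50: the average SVR is at most (0.70 + 0.70 + 0.40)/3 = 0.60, because D.13 gives the TAU rate as 40% or lower. Failures are therefore at least 50 × 0.40 = 20.

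The first assumption for the earlier regimens gives a total below 5 + 12.5 = 17.5. The second gives no ceiling, because it adds a quantity below 5 to one of at least 20.

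**5. Number affected.** This is the part of that group with no chart result whose result the study then obtains. The documents do not give that share, so no count follows.

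**The case against.** The strongest case against is that this is a query rather than a gap. Provision for releasing results would normally sit in the consent form or the Human Subjects section. Consent pages were removed from the supplied text, Table 1 points to the Human Subjects section, and D.5 shows that written consent already covers some uses and disclosures of health information. This stands, and it is why the fix is conditional.

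The rule also has an evident purpose. The six sources include urine tests for cocaine and opiates and computer-administered surveys of sensitive behaviour, and B.10 links take-home methadone doses to absence of illicit drug use. Keeping such data from providers protects participants. That supports the rule for toxicology and surveys. It gives no reason to include viral load and resistance, which clinicians already see whenever the chart holds them.

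A reader might infer that the protocol forbids clinicians from learning of treatment failure. It does not: the participant can authorise release in writing, and the clinician can test independently. A reader might also infer that no safeguard exists. The supplied text cannot show that.

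**Conclusion.** The point holds as a minor patient-safety improvement. Followed literally, D.10.4 can leave the on-site HCV clinician unaware of a viraemia or resistance result that only the study holds. This rests on reading the general rule as covering blood assays, which its position and wording support, and on no release provision existing in the documents not seen.

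The exposure is small, cannot be counted and may be zero. A reader might take the figures above to mean that up to 25 participants are affected. The documents do not support that, for two reasons: the TAU planning rate is 40% or lower, so 25 is not an upper bound even on participants without SVR; and only those who also lack a chart result are exposed. Nor is this a threat to the trial's inference: endpoints, alpha and power are unaffected.

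**What to change.** Amend D.10.4 along these lines: *Every participant is offered a written release at enrolment (or at the next research visit if already enrolled), which the participant may decline. Under it, study-run HCV viral load and resistance results go to the on-site HCV clinician when available. Urine toxicology and survey data remain under the non-release rule.*

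This keeps the principle of written permission but no longer relies on the participant to raise the matter. The cost is one or two sentences in D.10.4 and one consent line. The downside is slightly less confidentiality for virology results, limited by the right to decline. The offer should be the same in all three arms; clinicians already see chart virology in each of them, so the comparison should not be disturbed. If the consent form or Human Subjects section already provides this release, a cross-reference in D.10.4 is all that is needed.

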All	Adherence (self report)	Adult ACTG adherence instrument (167) Visual Analogue Scale (VAS) (168) 24 hour dietary recall instrument	0,4,8,12,24	Q

Q=Questionnaire

*All measures used in [name] pilot K23 HCV DOT study or [name] current R01 study

D. 10.3. Definitions of outcome measures.

Med-ic® or MEMS® missed dose adherence. For DAA and ribavirin (if applicable), adherence will be calculated as Med-ic blister pack dose openings divided by total number of prescribed doses in time interval. For example, Med-ic adherence for one week would be X/7Y, where X=number of Med-ic dose openings recorded in one week and Y=number of doses prescribed per day.

HCV treatment completion. Subjects will be considered to have completed treatment if they have completed at least 80% of the planned treatment course (at least 10 weeks of 12 week course, or at least 20 weeks of 24 week course) based on response guided therapy approach.^{98,115}

Sustained viral response (SVR). SVR is defined as undetectable HCV viral load 12 weeks after treatment completion or discontinuation.

Resistance. Subjects will be considered to have new drug resistance if they have a telaprevir- associated mutation (any substitutions at V36, T54, R155, A156) at any time point during the study, and the specific mutation did not exist at baseline. Subjects will be considered to have new drug resistance if they have a ledipasvir- associated mutation (K24R, M28T/V, Q30E/H/K/L/R, L31V/M/I, and Y93H/N) during the study, and the specific mutation did not exist at baseline. Subjects will be considered to have new drug resistance if they have a sofosbuvir- associated mutation (S282T) at any time point during the study, and the specific mutation did not exist at baseline.

Cost. Costs of HCV treatment will be collected using the same methods as in the pilot analysis (see Section D.1.8 above), by conducting chart reviews and assigning unit costs to all provider visits, lab tests, and medications based on Medicare fee schedules. The cost of the mDOT intervention will be determined by conducting observational time studies of the additional medical provider and patient time required for mDOT,

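### D.10.4 names only an NS3/4A resistance assay and takes the chart result first, while Table 3 lists NS3/4A, NS5A and NS5B for the same outcome

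*Combined protocol and SAP*

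**What the plan says.** Section D.10 of the combined protocol and SAP describes the resistance outcome in three places.

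- **D.10.3, definition.** New resistance means a mutation that was absent at baseline and falls in any of three lists: "if they have a telaprevir- associated mutation (any substitutions at V36, T54, R155, A156) at any time point during the study"; "ledipasvir- associated mutation (K24R, M28T/V, Q30E/H/K/L/R, L31V/M/I, and Y93H/N) during the study"; "sofosbuvir- associated mutation (S282T) at any time point during the study". No list is restricted to participants who took the drug concerned.
- **Table 3, measure.** The entry is "HCV GenoSURE NS3/4A, NS5A, NS5B (Monogram"), with chart and blood as sources, at weeks 4, 8, 12 and 24 and at follow-up weeks 4, 12 and 24.
- **D.10.4, data sources.** Under Medical record: "HCV viral load and resistance assays (if no SVR) will be obtained when possible by chart review", and "HCV resistance is measured by the Monogram HCV GenoSURE NS3/4A assay, which is automatically run on any HCV viral load" of at least 2000 IU/ml. Under Blood: "HCV viral load and resistance assays will be performed if not available by chart review", followed by "For subjects who fail to achieve SVR, resistance testing will be performed on post-treatment specimen". Neither Blood sentence names an assay. The follow-up visit text in D.10.2 also puts the chart before the blood draw.

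D.7 plans for 100 of the 150 participants to be on ledipasvir and sofosbuvir, and D.9.6 puts all new enrolees on that regimen.

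**The concern.** D.10.4 and Table 3 cannot both be the operating rule. The only assay that D.10.4 names covers the region that B.7 links to protease inhibitors. D.10.3 was extended to ledipasvir and sofosbuvir mutations, and Table 3 carries two further regions, so the D.10.4 sentence looks like text left over from the telaprevir period.

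The chart-first rule gives the mismatch practical effect. A participant on ledipasvir and sofosbuvir who fails with a viral load of 2000 IU/ml or more would have an automatic NS3/4A report. Nothing in the plan says that this report is incomplete for that participant. Someone working from D.10.4 could record resistance as available and order nothing further. Baseline is exposed in the same way: D.10.3 needs proof that the mutation was absent at baseline, yet Table 3 schedules no week 0 resistance test, and the baseline blood is stored only for possible testing.

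At stake are the incidence of resistance and its relation to adherence (Aim 2), the resistance comparison between arms (Aim 1), and the resistance input to the cost-effectiveness model (D.12.6). Separately, because D.10.3 does not tie scoring to regimen, a new substitution at a telaprevir position would count as resistance in someone who never took telaprevir.

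**Working it through.** **Step 1. The plan's own rate.** D.13 gives 16% in each intensive arm and 30% in TAU, with 1:1:1 allocation. The mean is (16 + 16 + 30)/3 = 20.7%, or 31 of 150. D.12.3 gives about 20%, or 30 of 150. The two agree.

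**Step 2. Coverage, place by place.**

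| Place | Regions named | Covers the ledipasvir and sofosbuvir lists in D.10.3? |
|---|---|---|
| Table 3 | NS3/4A, NS5A, NS5B | Yes, by inference |
| D.10.4, Medical record | NS3/4A | No, by inference |
| D.10.4, Blood (both sentences) | none | Not determined |

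The inference is that B.7 ties NS3/4A to protease inhibitors, and that Table 3 lists two further regions alongside a definition extended to two further drugs. The documents nowhere state which region carries which mutation.

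**Step 3. Events exposed in the 100 ledipasvir/sofosbuvir participants.** Events = N × f × r, with N = 100 (D.7). The failure proportion f is 5%, the edge of the SVR of over 95% quoted in B.3 and D.9.6. The proportion of failures with resistance mutations, r, is 62% (B.7). That figure comes from a section on protease-inhibitor therapy, and using it here is an assumption.

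- f = 5%: 100 × 0.05 × 0.62 = 3.1
- f = 10% (assumed): 100 × 0.10 × 0.62 = 6.2
- f = 20% (assumed): 100 × 0.20 × 0.62 = 12.4

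For given f and r these are upper limits on what is missed. Nothing is lost if Table 3 is followed. A failure below 2000 IU/ml has no automatic chart report to stand in the way of a study assay.

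**Step 4. Effect on Aim 2 incidence.** Apply the plan's 20% to the other 50 participants (an assumption): 10 events. With complete testing at f = 5%, the count is 10 + 3.1 = 13.1, and 13.1/150 = 8.7%. If the 3.1 are missed, it is 10/150 = 6.7% (exact 95% CI 3.2% to 11.9%).

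**Step 5. Outer bound.** If 20% of both regimen groups developed resistance, the true count would be 30/150 (20.0%, CI 13.9% to 27.3%). Missing all of it in the 100 would leave 10/150. That requires 20 resistant participants among 100, hence at least 20 failures and an SVR of at most 80%. With r = 62% it requires 20/0.62 = 32 failures, an SVR of about 68%.

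**Step 6. The Aim 1 comparison.** For a three-arm chi-square test with 2 df and alpha 0.05 (assumed; the plan states none for the omnibus test), the noncentrality is n × Σ(p − p̄)²/[p̄(1 − p̄)]. With rates of 16/16/30% and 40 per arm this is 40 × 0.01307/0.1640 = 3.19, giving power of 34%; at 50 per arm, power is 41%. This agrees with the plan's statement that the comparison is underpowered.

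**The case against.** The best reply is that the plan already contains the right answer. Table 3 is the outcome table and names all three regions from both sources. D.10.3 carries the new mutations. D.10.4 also provides that "For subjects who fail to achieve SVR, resistance testing will be performed on post-treatment specimen", with no chart condition, which covers exactly the participants in question. On this view one descriptive sentence is out of date and staff would follow the table.

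Much of that stands. A reader might infer that the plan cannot detect ledipasvir or sofosbuvir resistance at all, or that its sensitivity for it is zero. That is true, by inference, of the D.10.4 assay sentence read alone; it is not true of the plan as a whole. A reader might also infer that two thirds of the sample is misclassified. Resistance results are sought only without SVR, and the automatic assay needs a viral load of at least 2000 IU/ml, so only viraemic failures are exposed. Applying the plan's 16/16/30% rates to the 100 participants would give about 21 events, but that needs at least 21 failures, an SVR of 79% or lower, against the stated figure of over 95%. D.13 justifies its rates by earlier regimens and expects a smaller effect with ledipasvir and sofosbuvir.

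What does not stand is that the post-treatment sentence settles the matter. It names no assay, and the only assay named in D.10.4 is NS3/4A. As for telaprevir positions scored in unexposed participants, the baseline exclusion limits false positives and the documents give no rate, so no material harm from that is shown.

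**Conclusion.** D.10.4 contradicts Table 3 on how an Aim 1 and Aim 2 outcome is measured, and the chart-first rule could let the narrower assay close off the wider one. The point holds as an inconsistency with a plausible route to under-counting. It does not show that the plan is blind to resistance under the current regimen.

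On the documents' SVR figure the exposure is about 3 of 100 participants, and more if real-world failure is higher, which B.5 and B.6 leave open without giving a figure for this regimen. Three events are few, but at 5% failure they would be all the resistance expected in that group. The conclusion rests on three assumptions: the inferred link between mutations and regions, the borrowed 62%, and staff following D.10.4 rather than Table 3.

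The Aim 2 incidence and adherence analysis, the exploratory Aim 1 resistance comparison and the resistance input to the cost model are affected. Adherence, completion and SVR are not.

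**What to change.** 1. In D.10.4, replace the single-region assay with the three regions in Table 3.
2. State that a chart resistance result counts as available only if it covers every region relevant to the participant's regimen. Otherwise, test the missing regions on the post-treatment specimen and on the stored baseline blood, so that the baseline exclusion in D.10.3 can be applied.
3. Name the assay in the sentence on post-treatment testing of participants without SVR.
4. In D.10.3, score new resistance only at positions for drugs the participant received.

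The cost is a wording change in two sections and a few NS5A and NS5B assays on failures and their baseline samples. Table 3 already lists both assays. The change should be made before resistance is scored.
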